## **7.3 Disposition of Subjects**

### **7.3.1 Study Information**

Analysis Set: All Subjects Who Signed the Informed Consent Form  
Analysis Variable(s): Date First Subject Signed Informed Consent Form  
Date Last Subject Completed Study Drug Administration  
MedDRA Version  
SAS Version Used for Creating the Datasets  
Analysis Method(s): The following analysis will be performed for the above analysis variables.  
(1) Display of analysis variables

### **7.3.2 Subject Eligibility**

Analysis Set: All Subjects Who Signed the Informed Consent Form  
Analysis Variable(s): Randomization [Eligible for Randomization, Not Eligible for Randomization]  
Primary Reason for Subject Not Being Eligible [Adverse Event, Death, Lost to Follow-up, Protocol Deviation, Sufficient Subject, Screening Failure, Study Termination by Sponsor, Voluntary Withdrawal, Other]  
Analysis Method(s): The following analysis will be performed for the above analysis variables.  
When calculating percentages for the primary reasons for subject not eligible for randomization, the total number of subjects who were not eligible for randomization will be used as the denominator.  
(1) Frequency distributions

### **7.3.3 Disposition of Subjects**

Analysis Set: All Subjects Who Were Eligible for Randomization  
Analysis Variable(s): Study Completion Status [Completed All Planned Study Visits, Did Not Complete All Planned Study Visits]  
Reason for Discontinuation of Study Visits [Adverse Event, Death, Lost to Follow-up, Protocol Deviation, Study Termination by Sponsor, Voluntary Withdrawal, Other]  
Analysis Method(s): The following summaries will be provided by treatment group and by combining the treatment groups. When calculating percentages for the primary reasons for subject who did not complete all planned study visits, the total number of subjects who did not complete all planned study visits will be used as the denominator.  
(1) Frequency distributions

### **7.3.4 Protocol Deviations and Analysis Sets**

#### *7.3.4.1 Protocol Deviations*

Analysis Set:	All Subjects Who Were Eligible for Randomization
Analysis Variable(s):	Protocol Deviations [Deviations of Protocol Entry Criteria, Deviations Concerning Excluded Medication or Therapy, Noncompliance with Protocol, Deviations Related to Treatment Procedure or Dose, Deviations of Discontinuation Criteria, Major GCP Violations]
Analysis Method(s):	
The following summaries will be provided by treatment group and by combining the treatment groups.
 
The number of subjects with protocol deviations will be calculated and the details of deviations will be shown after classifying the contents of deviations into the above categories. A subject who has several categories will be counted once in each appropriate category.
 
(1) Frequency distributions

#### *7.3.4.2 Analysis Sets*

Analysis Set:	All Subjects Who Were Eligible for Randomization
Analysis Variable(s):	Handling of Subjects in Analysis Sets [Categories are based on the specifications in the List of Subject Evaluability Assignments]
	Inclusion/Exclusion of Analysis Set
	Safety Analysis Set [Included]
	PK Analysis Set [Included]
Analysis Method(s):	
The following summaries will be provided by treatment group for (1), and by treatment group and by combining the treatment groups for (2).
 
For (1), a subject who has several categories will be counted once in each appropriate category.
 
(1) Frequency distributions for handling of cases in each analysis set
 
(2) Frequency distributions for number of cases included in each analysis set

### **7.4 Demographic and Other Baseline Characteristics**

Analysis Set:	Safety Analysis Set
	PK Analysis Set

Analysis Variable(s):	Age (years) Height (cm) Weight (kg) (prior to administration in Period 1) BMI (kg/m  ) (prior to administration in Period 1) Smoking Classification Alcohol Classification Caffeine Classification	[The subject has never smoked, The subject is a current smoker, The subject is an ex-smoker] [Everyday, 2 to 3 Days a Week, 2 to 3 Days a Month, Never] [Yes, No]
Analysis Method(s):	The following summaries will be provided by treatment group and by combining the treatment groups. (1) Frequency distributions for categorical variables and descriptive statistics for continuous variables	

## **7.5 Medical History and Concurrent Medical Conditions**

Not applicable in this study.

## **7.6 Medication History and Concomitant Medications**

Not applicable in this study.

## **7.7 Study Drug Exposure and Compliance**

Not applicable in this study.

## **7.8 Efficacy Analysis**

### **7.8.1 Primary Efficacy Endpoint**

Not applicable in this study.

### **7.8.2 Secondary Efficacy Endpoint**

Not applicable in this study.

### **7.8.3 Additional Efficacy Endpoint**

Not applicable in this study.

## **7.8.4 Statistical/Analytical Issues**

### *7.8.4.1 Adjustments for Covariates*

Not applied in this study.

### *7.8.4.2 Handling of Dropouts or Missing Data*

Missing test results or data determined to be non-evaluable according to this Statistical Analysis Plan will not be used for hypothesis testing and estimations.

Values below the lower limit of quantification in drug concentrations and laboratory test values will be treated as zero, and values above the upper limit of quantification in laboratory test values will be treated as the upper limit of quantification.

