3.0 SCHEDULE OF STUDY PROCEDURES (PERIOD 1 AND PERIOD 2)

Study Day:	Screening		Treatment (a) (Period 1 and Period 2)				
	Days -28 to -2 (Screening)	Day -1 (Admission)	Day 1	Day 2	Day 3 (Discharge)	Early Termination	Day 6 (b) (Follow-up)
Hospitalization		X	X	X	X		
Informed consent	X						
Inclusion/exclusion criteria (c)	X		X				
Demographics and medical history	X						
Medication history	X						
Physical examination (d)	X	X	X	X	X	X	X
Vital signs (e)	X		X	X	X	X	X
Weight, BMI and height (f)	X		X		X		X
Concomitant medications	X	X	X	X	X	X	X
12-lead ECG (g)	X		X		X	X	X
Laboratory tests (h)	X		X	X	X	X	X
Urine drug and alcohol screen tests	X						
Immunology tests	X						
Study drug administration			X				
Plasma concentrations (i)			X	X	X	X (j)	
AE assessment (k)	X	X	X	X	X	X	X

- (a) There will be at least 6-day washout interval between the study drug administrations in Periods 1 and 2.
- (b) The examinations scheduled on the day before the study drug administration (Day -1) in Period 2 can be replaced with the follow-up examinations (Day 6) in Period 1, provided that they are scheduled on the same day.
- (c) Check of the inclusion/exclusion criteria will be done at Screening and before the study drug administration in Period 1 and not be done in Period 2.
- (d) Physical examination will be performed at Screening, Day -1, predose, 4, 24, 48 hours postdose and Day 6.
- (e) The sitting blood pressure (resting more than 5 minutes), sitting pulse rate, and body temperature (axillary) will be measured at Screening, predose, 4, 24, 48 hours postdose and Day 6.
- (f) Weight will be measured at Screening, predose, 48 hours postdose and Day 6. Height will be measured only at Screening for calculation of BMI.
- (g) The 12-lead ECG will be measured at Screening, predose, 48 hours postdose and Day 6.
- (h) Laboratory tests include hematology, serum chemistry, and urinalysis. Blood samples will be collected at Screening, predose, 24, 48 hours postdose and Day 6 after fasting for at least 8 hours.
- (i) PK blood samples will be collected at predose (from waking-up to immediately before the study drug administration) and 0.5, 1, 1.5, 2, 2.5, 3, 3.5, 4, 5, 6, 8, 12, 16, 24, and 48 hours postdose.
- (j) Measured only if the subject discontinues the study within 48 hours after the study drug administration.
- (k) The collection of AEs will commence from the time the subject signs the informed consent at Screening and continue until the follow-up examination in Period 2.

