## **6.0 DETERMINATION OF SAMPLE SIZE**

A total of 12 subjects (6 per sequence)

[Sample size justification]

A total of 12 subjects, with 6 subjects in each sequence, were considered sufficient sample size to evaluate the PK and safety of TAK-536. The sample size is not based on statistical considerations.

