## 7.0 METHODS OF ANALYSIS AND PRESENTATION

### 7.1 General Principles

#### 7.1.1 Study Definitions

- Treatment-emergent adverse event (TEAE): Adverse events that occurred after the start of the study drug administration
  - \* Among the TEAEs, those that occurred from the start of the study drug administration in Period 1 to before the start of the study drug administration in Period 2 are deemed as “TEAEs that occurred in Period 1” and those that occurred after the start of the study drug administration in Period 2 as “TEAEs that occurred in Period 2.”
- Pretreatment event(PTE):Adverse events that occurred after obtaining the consent but before the start of the study drug administration
- Descriptive statistics: Number of subjects, mean, standard deviation, maximum, minimum, and quartiles
- Coefficient of variation (CV)(%): Standard deviation / Mean x 100
- QTcF interval: QT interval corrected with Fridericia’s correction
- Treatment conditions:
  - Single oral dose under fasted condition
  - Single oral dose under fed condition
- Treatment group:
  - A (Single oral dose under fasted condition → Single oral dose under fed condition)
  - B (Single oral dose under fed condition → Single oral dose under fasted condition)

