#### **7.11.2.2 Urinalysis**

Analysis Set: Safety Analysis Set  
Analysis Variable(s): Specific Gravity  
pH  
Glucose  
Protein  
Blood  
Ketone Body  
Bilirubin  
Urobilinogen  
Categories: Results of determination based on reference values  
[Below lower limit of reference value,  
Within the range of reference value,  
Over upper limit of reference value]  
Visit: Predose, 24 and 48 Hours Postdose, Follow-up Examination (Day 6)  
Analysis Method(s): For specific gravity, summaries (1) to (3) will be provided by treatment condition.  
For each variable other than specific gravity, summary (3) will be provided by treatment condition.  
(1) Descriptive statistics for observed values for each visit and changes (each visit after administration-predose) will be provided.  
(2) Case Plots  
(3) A shift table for each visit before and after administration will be provided for the results of determination based on the reference values.

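### The SAP's zero rule for below-limit laboratory values also covers urine specific gravity, where zero is physically impossible; the defect is latent and of low severity

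*SAP*

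**What the plan says.** SAP 7.8.4.2 has one substitution rule for both kinds of measurement: "Values below the lower limit of quantification in drug concentrations and laboratory test values will be treated as zero". At the other end, "values above the upper limit of quantification in laboratory test values will be treated as the upper limit of quantification". Neither document gives a different rule for any single test. Protocol 11.1.3 leaves missing-data handling for the PK analysis to the SAP.

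Urinalysis falls within the rule, because the notes to the schedule in Protocol 3.0 say: "Laboratory tests include hematology, serum chemistry, and urinalysis".

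SAP 7.11.2.2 treats one urinalysis variable numerically: "For specific gravity, summaries (1) to (3) will be provided by treatment condition". Summary (1) reads "Descriptive statistics for observed values for each visit and changes (each visit after administration-predose) will be provided", summary (2) is case plots and summary (3) is the shift table. The remaining variables, pH included, are handled differently: "For each variable other than specific gravity, summary (3) will be provided by treatment condition". SAP 7.1.1 fixes the content of summary (1): "Descriptive statistics: Number of subjects, mean, standard deviation, maximum, minimum, and quartiles".

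**The concern.** Zero is a sensible stand-in for a drug concentration too low to measure, since the true value can be close to zero. Specific gravity is density relative to water, so urine cannot fall meaningfully below 1.000. (This follows from the definition of the quantity; the documents do not state it.) A result reported as below, say, 1.005 lies between 1.000 and 1.005, yet the rule enters it as 0. That is an error of about one whole unit on a scale where subjects differ by thousandths.

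At stake are the specific gravity mean, SD, minimum, change from predose and case plots for the condition and visit concerned. They belong to a secondary safety endpoint. If the value is noticed only after the tables are produced, it has to be corrected after the data have been seen.

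**Working it through.** The plan states no figure on this point, so there is none to reproduce.

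**Inputs from the documents.** Up to 12 subjects per treatment condition (2×2 crossover, 6 per sequence, SAP 6.0). Below-limit laboratory values become 0 (SAP 7.8.4.2). Visits are predose, 24 h, 48 h and Day 6 (SAP 7.11.2.2).

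**Assumed inputs, not in the documents.** The other 11 values have mean m = 1.010 to 1.020 and SD s = 0.004 to 0.008. The limit L is 1.000 or 1.005. A limit of 1.000 serves only as the end of the range, since no real result could lie below it.

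**Observed values at one visit, n = 12, one value coded c (either 0 or L).**

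- Mean = (11m + c)/12
- SD = √[(10/11)s² + (m − c)²/12]

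For m = 1.015, s = 0.006:

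- c = 0: mean = 11.165/12 = 0.930; SD = √(0.0000327 + 0.0858521) = 0.293.
- c = 1.005: mean = 12.170/12 = 1.014; SD = √(0.0000327 + 0.0000083) = 0.0064.
- Ratio of SDs: 0.2931/0.0064 ≈ 46.

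| m, s | Coded 0: mean, SD | Coded 1.000: mean, SD | Coded 1.005: mean, SD | SD ratio, zero to limit |
|---|---|---|---|---|
| 1.010, 0.004 | 0.926, 0.292 | 1.009, 0.0048 | 1.010, 0.0041 | 61 to 72 |
| 1.015, 0.006 | 0.930, 0.293 | 1.014, 0.0072 | 1.014, 0.0064 | 41 to 46 |
| 1.020, 0.008 | 0.935, 0.295 | 1.018, 0.0096 | 1.019, 0.0088 | 31 to 34 |

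Under the zero rule the SD is close to m/√12 ≈ 0.29 whatever the true spread, so the assumed s hardly matters. With 10 subjects the mean is 0.909 to 0.918 and the SD 0.319 to 0.323.

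In the first two rows, with a limit of 1.005, the lowest of the 11 spread values (1.0032 and 1.0047) also falls just under the limit. It was left as it is, so that exactly one value is substituted.

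**Change from predose.** Take the affected subject's predose value as m and the other 11 subjects as unchanged.

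- Coded 0: mean change = −m/12 = −0.084 to −0.085; SD = m/√12 = 0.292 to 0.294.
- Coded at the limit: mean change = −(m − L)/12 = −0.0004 to −0.0017; SD = 0.001 to 0.006.

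If the zero falls at predose, that subject's change is about +1.015 at each later visit. This adds about 1.015/12 = 0.085 to the mean change at 24 h, 48 h and Day 6.

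**What does not move.** The below-limit value ranks lowest whether coded 0 or L, so the median and lower quartile are the same either way. In the shift table it would most likely still be classed as below the reference range.

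**The case against.** The strongest objection is that the rule may never act. The documents give no quantification limit for specific gravity and do not say that the local laboratory reports it as less than some value. This stands: the defect is in the rule and is not a demonstrated error in any table.

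The consequences are also contained. Specific gravity is one descriptive variable in a secondary endpoint, and a minimum of 0 would be conspicuous in a table of 12. This stands too and lowers the severity. It does not make the rule right, because whenever the rule acts on specific gravity it gives an impossible number.

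Four stronger readings are tempting, and the documents do not support them:

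- **That it will happen often.** Some assumed settings (limit 1.003 to 1.005, mean 1.015 to 1.018, SD 0.006 to 0.007) put at least one censored value in 18% to 44% of 12-subject cells. None of these inputs is in the documents, and the range properly starts at 0%. Protocol Appendix B has the 24 h and 48 h urine collected from waking, and Protocol 9.2.8 requires an overnight fast, so dilute samples may be rarer than assumed.
- **That it produces a false food effect.** No fed-minus-fasted contrast is planned for laboratory data; SAP 7.9.1.3 models PK parameters only.
- **That the two halves of the sentence contradict each other.** Zero is a natural lower bound for many quantities and there is no natural upper one, so different treatment at the two ends is not in itself inconsistent.
- **That serum chemistry is materially distorted.** For a test with a true zero the error is at most the limit, and no analyte or size can be shown from the documents.

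**Conclusion.** The point holds as a conditional one. As written, SAP 7.8.4.2 covers specific gravity, and one below-limit result in a 12-subject cell would give a mean of 0.926 to 0.935, an SD of 0.292 to 0.295 (31 to 72 times too large), a minimum of 0 and a mean change of about -0.084 to -0.085. These sizes rest on the assumed mean, SD and limit but barely vary across them. Whether the rule is ever triggered depends on the local laboratory's reporting, which the documents do not describe.

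Severity is low. The output is descriptive, no decision rule depends on it, and the plasma-concentration part of the rule is not in question. The correction is worth making because it is cheap.

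**What to change.** In SAP 7.8.4.2, confine the zero rule to plasma drug concentrations. For laboratory tests, state that a value below the lower limit of quantification is set to that limit, matching the existing treatment at the upper limit. If the sponsor prefers to leave the rule for other tests alone, the minimum change is to do this for specific gravity only.

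The cost is one sentence before database lock, with no effect on the PK analysis. Censored laboratory values are then slightly overstated, by no more than the gap below the limit. For specific gravity with an assumed limit of 1.005, that is at most 1.005 − 1.000 = 0.005 per value, or 0.005/12 ≈ 0.0004 in a 12-subject mean. Asking the local laboratory whether it reports specific gravity as below a limit would show whether the rule can act at all.

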### *7.8.4.3 Multicenter Studies*

Not applied in this study.

### *7.8.4.4 Multiple Comparison/Multiplicity*

Not applied in this study.

### *7.8.4.5 Use of an "Efficacy Subset" of Subjects*

Not applied in this study.

### *7.8.4.6 Active-Control Studies Intended to Show Equivalence or Non-Inferiority*

Not applied in this study.

### *7.8.4.7 Examination of Subgroups*

Not applied in this study.

## 7.9 Pharmacokinetic/Pharmacodynamic Analysis

### 7.9.1 Pharmacokinetic Analysis

#### 7.9.1.1 Plasma Concentrations

Analysis Set: PK Analysis Set  
Analysis Variable(s): Plasma Concentrations of TAK-536  
Visit: Predose, 0.5, 1, 1.5, 2, 2.5, 3, 3.5, 4, 5, 6, 8, 12, 16, 24, and 48 Hours  
Postdose  
Analysis Method(s): The following analysis will be performed for the above analysis variables.  
(1) Descriptive statistics will be provided for each treatment condition by visit.  
(2) Mean and standard deviation will be plotted simultaneously for both treatment conditions (vertical axis: normal scale).  
(3) Mean will be plotted simultaneously for both treatment conditions (vertical axis: common logarithmic scale).

#### 7.9.1.2 Pharmacokinetic Parameters

Analysis Set: PK Analysis Set  
Analysis Variable(s): Pharmacokinetic Parameters of TAK-536  
Cmax tmax AUClast  
AUCinf t1/2z MRTlast,ev  
MRTinf,ev Lambda z CL/F  
Vz/F  
Analysis Method(s): The following analysis will be performed for the above analysis variables by treatment condition.  
(1) Summary of Pharmacokinetic Parameters  
For Cmax, AUClast, and AUCinf, descriptive statistics, geometric mean, and CV will be provided.  
For Tmax, descriptive statistics will be provided.  
For all other variables, descriptive statistics and CV will be provided.

#### 7.9.1.3 Assessment of Food Effect

Analysis Set: PK Analysis Set  
Analysis Variable(s): Pharmacokinetic Parameters of TAK-536  
Cmax tmax AUClast  
AUCinf t1/2z MRTlast,ev  
MRTinf,ev Lambda z CL/F  
Vz/F  
Analysis Method(s): The following analysis will be performed for the above analysis variables.

- (1) The difference in the least square means between treatment conditions (single oral dose under fed condition – single oral dose under fasted condition) and the two-sided 90% confidence interval will be provided using a crossover ANOVA model. The ANOVA model will include log-transformed (natural log) analysis variables other than tmax as the dependent variable, and treatment condition, treatment group, and period as independent variables.
- (2) The difference in the least square means between treatment conditions (single oral dose under fed condition – single oral dose under fasted condition) and the two-sided 90% confidence interval will be provided using a crossover ANOVA model. The ANOVA model will include non-natural log-transformed tmax as the dependent variable, and treatment condition, treatment group, and period as independent variables.

#### *7.9.1.4 Individual Plasma Concentrations*

Analysis Set: All Subjects Who Entered the Treatment Period  
Analysis Variable(s): Plasma Concentrations of TAK-536  
Visit: Predose, 0.5, 1, 1.5, 2, 2.5, 3, 3.5, 4, 5, 6, 8, 12, 16, 24, and 48 Hours Postdose  
Analysis Method(s): The following analysis will be performed for the above analysis variables.  
(1) Individual plasma concentrations will be plotted simultaneously for both treatment conditions (vertical axis: normal scale).

#### *7.9.1.5 Subject Data Listings for Pharmacokinetic Parameters*

Analysis Set: All Subjects Who Entered the Treatment Period  
Analysis Variable(s): Pharmacokinetic Parameters of TAK-536  
Cmax tmax AUClast  
AUCinf t1/2z MRTlast,ev  
MRTinf,ev Lambda z  
Measuring points of estimating Lambda z (start point, end point, and number of points) and adjusted R-squared contribution rate  
CL/F Vz/F  
Analysis Method(s): Subject data listings including the following variables will be displayed.  
(1) Subject ID, subject number, treatment group, treatment condition, and timing

### **7.9.2 Pharmacodynamic Analysis**

Not applicable in this study.

### **7.10 Other Outcomes**

Not applicable in this study.

## 7.11 Safety Analysis

### 7.11.1 Adverse Events

#### 7.11.1.1 Overview of Treatment-Emergent Adverse Events

Analysis Set: Safety Analysis Set  
Analysis Variable(s): TEAE  
Categories: Relationship to Study Drug [Related, Not Related]  
Intensity [Mild, Moderate, Severe]  
Analysis Method(s): The following analysis will be performed for the above analysis variables by treatment condition.

- (1) Overview of TEAE
  - 1) All TEAEs (number of events, number and percentage of subjects)
  - 2) Relationship of TEAEs to study drug (number of events, number and percentage of subjects)
  - 3) Intensity of TEAEs (number of events, number and percentage of subjects)
  - 4) TEAEs leading to study drug discontinuation (number of events, number and percentage of subjects)
  - 5) Serious TEAEs (number of events, number and percentage of subjects)
  - 6) Relationship of serious TEAEs to study drug (number of events, number and percentage of subjects)
  - 7) Serious TEAEs leading to study drug discontinuation (number of events, number and percentage of subjects)
  - 8) TEAEs resulting in death (number of events, number and percentage of subjects)

TEAEs will be counted according to the rules below. When calculating percentages for TEAE, the number of subjects who were treated by the study drug under that treatment condition in the safety analysis set will be used as the denominator.

[Number of subjects with TEAEs]

- In case of “frequency distributions by relationship to study drug”  
A subject with occurrences of TEAE in both categories (i.e., Related and Not Related) will be counted once in the Related category.
- In case of “frequency distributions by intensity”  
A subject with multiple occurrences of TEAE will be counted once for the TEAE with the maximum intensity.
- In case of distributions other than the above  
A subject with multiple occurrences of TEAE will be counted only once.

[Number of events]

For each summary, the total number of events will be calculated.

